5. SUBJECT POPULATION

Number of Subjects: This study includes three sets of subjects, including (1) youth patients, (2) parents, and (3) their respective adult support team members. The subject population is the same for both phases one and two.

• Youth patients: We will enroll approximately n = 60-70 total adolescent patients in the Child and Adolescent Partial Hospitalization Service (CAPHS). The first n = 5-10 of these will be used to refine and optimize the feasibility and acceptability of YST+YM. All

Page 4 of 64 Version Date: 12/13/21 subjects will be used to evaluate target engagement. Based on consultation with CAPHS clinical director, [name] (LMSW-R), greater than 80% of patients are expected to be eligible for participation. Of eligible patients, roughly 50% are estimated to enroll in the study. Again based on consultation with [name], 75% of the initially enrolled patients are expected to complete the study. Thus, we will screen approximately 165 patients to identify 130 eligible subjects, of which 65 are expected to enroll. Given low attrition for comparable clinical programs in CAPHS (i.e., a year of pilot implementation of traditional YST in that clinic), we conservatively estimate a 25% attrition rate. Attrition will be handled with an intent-to-treat design. Given these considerations, we anticipate n = 50 subjects will provide follow-up data, providing a sufficient sample size to detect a signal for intervention target engagement.

- Parents / legal guardians: We will invite one parent / legal guardian per enrolled youth to provide feedback on the intervention, proxy-ratings of the youth's emotional well-being, as well as self-report of their own well-being. Based on consultation with clinic staff who regularly interact with this population, recruitment and retention rates for parents are expected to be roughly 80% per youth who completes the study. Thus, for the roughly n = 50 youth subjects who provide full follow-up data, we expect roughly n = 40 parents / guardians to complete all measures. This is a sample size sufficient to refine the intervention with informal feedback and to further evaluate target engagement as assessed by proxy-report.

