Youth-focused Module (YM): The YM consists of three remote sessions involving the youth and 12 weekly text message prompts encouraging the subject to reflect on their usage of content from the YM. The first session occurs before discharge and will be either in-person or remote, depending on current clinic policy and patient/interventionist availability. The first session includes only the patient and the interventionist. The second (post-discharge weeks 4-6) and third (post-discharge weeks 10-12) sessions happen after discharge and will all be remote. For these post-discharge sessions, youth subjects will also be encouraged, but not required, to invite one or more members of their support team. The YM content is strengths-based and centers on seeking social connection, emotional balance, and purpose/meaningful activities. [name] will supervise the treatment through regular review of audiotapes (random sample of 20% of sessions) to ensure fidelity.

Page 15 of 64 Version Date: 12/13/21 • Text Messages: Subject identifying information, clinical symptoms (including suicide risk) and PHI is not exchanged in the text messages themselves. Detailed information about text messaging is included under the "Privacy and Confidentiality of Subjects and Research Data" section. Privacy and security risks associated with text messaging are described in detail to all subjects during assent / consent, including the inherent unprotectability of text-message data and the option to automatically withdraw from texts at any time with the phrase "unsubscribe".

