15. SUBJECT WITHDRAWALS

Youth psychiatric re-hospitalization: Subjects will be withdrawn from the study and from treatment if they are hospitalized for psychiatric concerns (e.g., suicide attempt, manic episode). Under these conditions subjects (a) will likely be in sufficient distress that they can no longer maintain assent for participation and (b) require more immediate and intensive care than is appropriate for subjects in YST+YM. Non-psychiatric hospitalization (e.g., broken bone, chronic medical condition) will not trigger withdrawal from the study.

Youth failure to complete treatment: Youth subjects will have 14 weeks from the time of discharge to complete the 3 sessions of the YM module in the YST+YM treatment. Patients that have not completed these three sessions after 14 weeks will have their treatment terminated, but will still be allowed to complete any remaining assessments in the study.

Parent / legal guardian withdrawal: Any parents / guardians who wish to withdraw from the study will be allowed to do so at no penalty to themselves or their children. If a parent / guardian wished to withdraw but still allow their child to participate, that youth will still be allowed to continue independently.

Adult failure to complete treatment: Adult support team subjects will have 14 weeks from the time of discharge to complete the 12 YST-based phone check-in sessions with study staff. Subjects that have not completed these sessions after 14 weeks will have their support team role terminated, but will still be allowed to complete any remaining assessments in the study.

Failure to establish adult support team: The YST+YM intervention requires community adults

Page 19 of 64 Version Date: 12/13/21 to commit to providing 12 weeks of social support to a teen in psychiatric distress. Even when the youth subject makes several nominations, it is possible none of the adults they nominated will be able to join the intervention. If study staff are unable to confirm at least one supportive adult is willing to serve on a subject's support team by 2 weeks after the patient's discharge date, that subject will be withdrawn from the study.

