Partial withdrawal: Subjects who wish to withdraw from the intervention, but continue assessments will be allowed to do so. They will be compensated at the same rate for all remaining assessments. Subjects who wish to withdraw from the assessments, but remain in the intervention will be allowed to do so. However, they will only be compensated for assessments they have already completed. Attempts will be made to add a replacement subject to the study in all of these cases, as long as there is sufficient funding and study time remaining to do so.

Data use after withdrawal: Unless otherwise requested by the subject at the time of withdrawal, all available data will be retained and integrated into subsequent analysis.

Sample size maintenance: Study staff will attempt to replace any withdrawn youth subjects with the next available patient - as long as there is sufficient time remaining in the study (i.e., at least 6 months) for new subjects to complete the intervention and all assessments. No replacement attempts will be made for adult support team members who withdraw.

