17. DATA ANALYSIS PLAN

For Aim 1, we will use descriptive statistics to gauge achievement of feasibility and acceptability thresholds for patients. Means above 3.5 (on a 5 point scale) will be regarded as adequate feasibility and acceptability.

For Aim 2, a linear mixed effects model will be used to evaluate (a) overall frequency of responding to text messages and (b) trends in text response rates over time. Aim 2 will also utilize generalized linear mixed effects models (fixed effect for time, with a random effect for individual) to evaluate changes in intervention target scores over time. Each of the intervention targets will serve as the outcome variable in its own separate model.

For Aim 3, means and proportions will be estimated and retained for future study planning.

A power analysis evaluating these models was conducted via simulation. For the linear mixed effects models (Aims 2), assuming a moderate effect size (d = .50) and moderate within-subject shared variance attributable (ICC = .05), simulations show this model will have adequate power (.82) to detect target engagement over the course of the intervention. Because Aims 1 and 3 utilize only descriptive statistics and require no statistical inference, no power analysis was conducted.

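### Youth with no confirmed adult two weeks after discharge leave the study, not only the intervention, so their later outcomes are never collected and no planned measure records the failure to form a team

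*Combined protocol and SAP*

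**What the plan says.** The rule is in Section 15 (Subject Withdrawals), under failure to establish an adult support team. It applies when staff prove "unable to confirm at least one supportive adult is willing to serve on a subject's support team by 2 weeks after the patient's discharge date", and its consequence is that "that subject will be withdrawn from the study". The paragraph on sample size maintenance in the same section adds: "Study staff will attempt to replace any withdrawn youth subjects with the next available patient", provided at least six months of study time remain.

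Four other statements bear on this:

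- Section 15, data use after withdrawal: unless the subject asks otherwise, "all available data will be retained and integrated into subsequent analysis".
- Section 15, youth who do not finish the three sessions within 14 weeks: treatment ends, but they "will still be allowed to complete any remaining assessments in the study". Under partial withdrawal, a youth who chooses to leave the intervention may also stay in the assessments.
- Section 5: "Attrition will be handled with an intent-to-treat design". The same section plans to use every enrolled youth to evaluate target engagement.
- Section 17, Aim 1: "Means above 3.5 (on a 5 point scale) will be regarded as adequate feasibility and acceptability". No other feasibility criterion is given.

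**The concern.** The intervention works through a team of adults, and feasibility is a stated purpose of the pilot. An enrolled youth for whom no adult comes forward is a direct feasibility result. Under the rule that youth's follow-up stops, a new patient may be enrolled, and no planned outcome counts the event.

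The loss is also selective. Aim 2 concerns contact with supportive adults and perceived support, and youth whose nominees all decline plausibly have less support available. If they are not followed, the later Aim 2 scores describe youth with at least one adult. The same holds for Aim 3, whose estimates of depression, anxiety, ideation and attempts are meant for planning later trials. A later trial that analyses everyone enrolled would include youth without a team, and this pilot would say nothing about their course.

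**Working it through.** **1. Order of events.** Consent, the baseline survey and the first session are planned before discharge (Section 9: "The first session occurs before discharge"). The deadline falls two weeks after discharge. These are therefore losses after enrolment and baseline, and they cost three of the four youth assessments (weeks 6, 12 and 24).

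**2. The plan's own recruitment figures (Section 5).** 165 × 0.80 = 132 (stated as 130 eligible). 130 × 0.50 = 65 enrolled. 65 × 0.75 = 48.75 (stated as 50 with follow-up). These reproduce. The implied loss is 65 − 48.75 = 16.25 youth. The plan does not say whether this includes youth withdrawn for lack of a team.

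**3. Joining rate.** Section 5 expects 2–3 adults to enrol for every 3–4 nominated, that is, 130–195 of 195–260. 130/195 = 0.67 and 195/260 = 0.75. The least favourable pairing, 2 of 4, gives 0.50.

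**4. Chance that no adult joins.** If nominees decide independently (an assumption), the chance is (1 − p)^k for k nominees with joining probability p. The last column multiplies it by 65.

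| p | k | (1 − p)^k | Expected of 65 |
|---|---|---|---|
| 0.75 | 4 | 0.4% | 0.3 |
| 0.75 | 3 | 1.6% | 1.0 |
| 0.67 | 4 | 1.2% | 0.8 |
| 0.67 | 3 | 3.7% | 2.4 |
| 0.50 | 4 | 6.3% | 4.1 |
| 0.50 | 3 | 12.5% | 8.1 |

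Section 6 admits youth who can name only two adults. For such a youth at p = 0.67 the chance is (1/3)² = 11%. This applies youth by youth and should not be multiplied by 65, because the plan is for 3–4 nominations.

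**5. Possible effect on Aim 2.** Take the d = 0.50 assumed in Section 17 for youth with a team, and assume no change in youth without one. With 2 of 65 affected, the all-enrolled effect is 0.50 × 63/65 = 0.485. With 8 affected, it is 0.50 × 57/65 = 0.438. The zero change is an illustration; the documents give no evidence on how these youth would change.

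**6. What retaining baseline data achieves.** The Aim 2 model has a fixed effect for time and a random effect for individual. A youth with only a baseline value shows nothing about his or her own change and enters only through the baseline level. A few such records add little to the time effect. In effect, the model takes their later course to be like that of youth with a team.

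**7. The feasibility criterion.** A mean rating is taken over those who give ratings. A youth withdrawn at two weeks gives none after session 1. The mean of later ratings would be the same whether no youth or eight failed to form a team, so the criterion cannot show the difference.

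**8. The rules side by side.** Unfinished sessions: treatment ends, assessments continue. Choosing to leave the intervention: assessments may continue. Psychiatric re-hospitalization: both end, with reasons given about assent and level of care. No team: both end, and the text explains why the intervention cannot run but gives no reason to stop assessments.

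**The case against.** A reader might infer that these youth are deleted from the sample and that the plan contradicts its own intent-to-treat statement. The documents do not support either reading. Section 15 keeps all available data after withdrawal unless the subject objects, so baseline and session-1 data stay in. Nothing excludes these youth from an analysis set or says that a replacement takes their place in a denominator. Replacement is an attempt, and a conditional one. What stands is narrower: the rule prevents the follow-up that intent-to-treat needs, and the analysis set and the status of replacements are undefined.

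The numbers may also be lower than in the table. The trigger is that no adult is confirmed as willing, which is easier to avoid than full enrolment, the event behind the 67–75%. The eligibility wording may also allow a parent to be one of the named adults. Against that, refusals that cluster within a family would raise the figures. Even 2 of 65 is small beside the planned 25% attrition.

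Testing target engagement in youth who can actually receive a team-based intervention is a defensible pilot choice, and Section 6 already excludes youth who cannot name two trusted adults. That supports a secondary analysis in youth with a team. It does not explain why follow-up of the others should stop or why their number should go unreported.

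Finally, follow-up costs more than a questionnaire. The week 6 and 12 surveys are given during intervention sessions, and all assessments are live with a safety review. This is correct and is reflected in the cost below.

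**Conclusion.** The point holds as a problem of follow-up and reporting. Followed as written, the rule loses every outcome after session 1 for enrolled youth whose team does not form. The neighbouring rules do not do this to other youth whose intervention ends, and the sole feasibility criterion does not register the event.

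The size is uncertain and probably small: about 0 to 2 of 65 youth at 67–75% joining with 3–4 nominees, and about 8 at 50% with three. Both figures rest on independent decisions and on joining rates taken from clinic experience quoted in Section 5. On the illustrative zero-change assumption, the Aim 2 effect would move from 0.50 to between 0.485 and 0.438.

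It is tempting to conclude that the results are biased in favour of the intervention. That direction is plausible, but the documents contain nothing on how youth without a team fare, so it is not shown. The stronger reason to act is that a direct feasibility failure has no place in the planned results.

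**What to change.** - **Section 15:** let youth with no confirmed adult by the deadline complete the week 6, 12 and 24 assessments, using the assessment-only route already open to other youth whose intervention ends. This changes data collection only and leaves the rule on the intervention itself untouched.
- **Sections 5 and 17:** define the Aim 2 and Aim 3 analysis sets as all enrolled youth. State that replacements are additional enrolments, added to the denominator, and do not substitute for those withdrawn.
- **Section 17, Aim 1:** add a feasibility outcome: youth with at least one confirmed adult divided by youth enrolled. Report the count with no team beside the mean ratings.

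**Cost:** three gift cards at $25, so up to 3 × $25 = $75 per affected youth. Each also needs three separately scheduled, staffed remote assessments with the existing safety review. The rest is wording. For the 0 to 2 youth expected under the plan's own joining rates this is a minor burden, and at 8 youth it would be 8 × 3 = 24 assessments.

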16. PRIVACY AND CONFIDENTIALITY OF SUBJECTS AND RESEARCH DATA

Data Storage & Confidentiality: In order to protect the **confidentiality of subject information**, we will take a number of precautions. These include training research interviewers in confidentiality procedures; entry and storage of data using coded identification labels; maintenance of project computers in secure locations with restricted access by enforced password protection; use of HIPAA compliant data management software (REDCAP). Back-ups of all study files will be made daily to allow for recovery of data due to disk failure. All data, including assessment measures, will be obtained with the documented eConsent of the patient. Information pertaining to individual subjects will be released with the patient's informed and written assent and parental consent only, except in unusual cases where withholding the information might pose a serious risk or danger to the subject or others. All data will be identified by a uniquely coded study number assigned to each subject. Access to the master list of study numbers will be restricted to [name] and study staff. Confidentiality will be further maintained by the storage of "hard copy" data in locked files in a locked office. Access to computerized data is restricted and subject to review by [name]. Publications or presentations will report only cumulative data or descriptions expected to maintain subjects' anonymity.

All **clinical data** collection involving human subjects will be HIPAA compliant. All clinical data involving human subjects will be stripped of any identifiers; the data will be stored in a secure HIPAA compliant program called REDCAP, which manages protected health information in a HIPAA compliant manner.

Text message communications may be sent or received in an unencrypted (unprotected) manner. Therefore, there is an inherent risk that the content of the communication, including subjects personal information, could be shared beyond the subject and the study team. To mitigate this risk to confidentiality:

• Subject information will not be entered into text messaging software (Twilio), unless they have provided explicit eConsent to receive text messages as part of the study.

- Subjects will be specifically notified of this risk during the assent / consent process and on the assent / consent form and reminded that this form of communication is not secure.
- We will never solicit any PHI from subjects via text message and will instruct them not to include PHI in their responses to text messages.
- All subjects will also have the opportunity to withdraw from the text message portion of the study at any time by replying to a study text with the phrase "unsubscribe" and this is made explicit in the assent / consent documentation. This withdrawal option will also be explained verbally to subjects during the assent / consent process and repeated during remote intervention sessions.
- At the conclusion of the study, all subject text message information will be downloaded and stored on a HIPAA-compliant storage platform supported by URMC (Box.com). Only the PI ([name]) will have access to this data. After text message data has been downloaded and stored on Box, it will be deleted from Twilio, which provides explicit options to permanently delete any subject's information.

Audio recordings of semi-structured interviews will be transcribed and then destroyed to protect the security and confidentiality of identifiable information. In order to protect subjects' **privacy**, audio-visual recordings will only be made with subjects' written assent / consent. Sessions will be audio recorded for supervision of study interventionists, to evaluate fidelity, and to further refine the intervention. The data on the recording will be identified only by an ID number. Recordings for the sessions will be uploaded onto UR Box.

In order to protect subjects' **privacy**, subjects will be free to refuse to answer any questions they would prefer to not answer and intervention sessions will be attempted in private settings, when possible. Subjects may be re-contacted in the future to update basic information, but will not be penalized for refusing such contact.

15. DATA / SAMPLE STORAGE FOR FUTURE USE

We are willing to share data with other researchers and have chosen measures that are useful for future analyses; however, the data sharing agreement involves sharing only de-identified data with other investigators and the use of data-sharing agreements that provide for: (1) a commitment to use the data only for research purposes and not to identify any individual subject; (2) a commitment to secure the data using appropriate computer technology; and (3) a commitment to destroy or return the data after analyses are completed.

16. DATA AND SAFETY MONITORING PLAN

Please refer to attached Data and Safety Monitoring Plan. Note, only youth subjects will be asked about safety-related issues. Adult support team members are only asked about feasibility and acceptability of the intervention.

Note, the intervention itself also involves acquiring a pre-existing safety plan from each youth and their therapist – all youths have these as a requirement of discharge from the CAPHS clinic. This safety plan will be stored on the HIPAA-compliant REDCap server. It will also be shared with parents and support team members.

17. DATA ANALYSIS PLAN

For Aim 1, we will use descriptive statistics to gauge achievement of feasibility and acceptability thresholds for patients. Means above 3.5 (on a 5 point scale) will be regarded as adequate feasibility and acceptability.

For Aim 2, a linear mixed effects model will be used to evaluate (a) overall frequency of responding to text messages and (b) trends in text response rates over time. Aim 2 will also utilize generalized linear mixed effects models (fixed effect for time, with a random effect for individual) to evaluate changes in intervention target scores over time. Each of the intervention targets will serve as the outcome variable in its own separate model.

For Aim 3, means and proportions will be estimated and retained for future study planning.

A power analysis evaluating these models was conducted via simulation. For the linear mixed effects models (Aims 2), assuming a moderate effect size (d = .50) and moderate within-subject shared variance attributable (ICC = .05), simulations show this model will have adequate power (.82) to detect target engagement over the course of the intervention. Because Aims 1 and 3 utilize only descriptive statistics and require no statistical inference, no power analysis was conducted.

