Aim 1 - To optimize YST+YM for feasibility and acceptability. Outcome: Semi-structured interviews and rating scales will identify the most and least preferred elements of the YM module. Response rates to automated text-messages will also be used to evaluate message appeal.

Aim 2 - To test target engagement: does YST+YM increase utilization of interpersonal emotionregulation strategies and social support among adolescents with recent suicidal ideation or attempts? Hypothesis: over 12 weeks of YST+YM, subjects will demonstrate increases in: (a) the number of weekly contacts initiated to supportive adults in their lives, (c) the utilization of interpersonal emotion regulation strategies, and (c) their perceived sense of social support. These gains will be maintained at 3-month post-intervention follow-up.

Aim 3: Estimate prevalence of clinical outcomes for planning of subsequent trials - what is the average rate of clinical over the course of intervention and through 3-month follow-up? Outcome: Estimates of changes in distal targets, including anxiety, depression, and suicidal ideation and attempts for the planning of larger subsequent trials.

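### Section 17 names a linear mixed model for text replies, which are naturally yes/no; a logistic mixed model fits better, and the model labels for replies, targets and power need tidying

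*Combined protocol and SAP*

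**What the plan says.** Section 17 (Data Analysis Plan) gives Aim 2 two kinds of model.

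- Text replies: "a linear mixed effects model will be used to evaluate (a) overall frequency of responding to text messages and (b) trends in text response rates". It does not say whether the outcome is a reply to a single prompt, a weekly rate or a count, and it gives no random-effects structure for this model.
- Targets: "Aim 2 will also utilize generalized linear mixed effects models (fixed effect for time, with a random effect for individual) to evaluate changes in intervention". The outcome is the score on each target, with one model per target. No family or link is named.

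On power it says: "A power analysis evaluating these models was conducted via simulation". It then refers to the linear mixed effects models for Aim 2, with d = .50 and ICC = .05, and states that "simulations show this model will have adequate power (.82) to detect target engagement over the course of the intervention". Sample size and alpha are not given there. Section 17 adds that Aims 1 and 3 use only descriptive statistics.

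Elsewhere, Section 9 describes "12 weekly text message prompts" per youth. The specific aims in Section 2 put replies under Aim 1: "Response rates to automated text-messages will also be used to evaluate message appeal". The Aim 2 hypotheses there are the number of weekly contacts initiated, use of interpersonal emotion regulation, and perceived social support.

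**The concern.** At one prompt a week, a youth either replies or does not, and any rate built from such replies lies between 0 and 1. A Gaussian model ignores both the bounds and the way the variance changes with the mean. The generalized model, which would suit replies, is given instead to targets of which two of three are scale scores. Only the contact count clearly calls for it.

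What is at stake is the reply trend, which Section 17 explicitly sets out to estimate. If engagement starts high and then fades, the interval around the estimated decline may be too narrow, and fitted rates for individual youths may be impossible values. There is also a plain inconsistency of place: Section 2 treats replies as an Aim 1 measure of appeal, while Section 17 analyses them under Aim 2.

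**Working it through.** **1. The plan's own figure.** Take a random-intercept linear mixed model for a continuous score, with a total change of 0.50 SD from week 0 to week 12. ICC = .05 and d = .50 come from Section 17. The expected enrolment of n = 65 comes from Section 5. Two-sided alpha .05 is assumed.

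- SE(slope) = sqrt((1 − ICC)/(n × Sxx)). Sxx = 72 for waves at weeks 0 and 12, and also for weeks 0, 6 and 12.
- SE = sqrt(.95/(65 × 72)) = 0.01425; slope = .50/12 = 0.04167; noncentrality = 2.92.
- Power = .821 (two waves, 64 df) or .827 (three waves, 129 df).

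So .82 is what a linear model of a continuous target score gives at full enrolment. The match is not unique: n = 50 with a one-sided test gives .81 to .82.

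**2. Why a linear model can understate the uncertainty of a reply trend.** On the logit scale a common decline gives different declines in probability. A fall of 0.6 in log-odds takes a youth at .50 (logit 0) to 1/(1 + e^0.6) = .354, a drop of .146. It takes a youth at .93 (logit 2.59) to logit 1.99, or .879, a drop of .051. A model with one intercept per youth and a common slope leaves this variation in slopes out of the standard error. With no trend there is no such variation.

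**3. Size, by simulation.** 65 youths × 12 yes/no replies, random-intercept logit truth, random-intercept linear model fitted. The 12 prompts come from Section 9. Youth SDs and reply rates are assumptions, since the documents give none.

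| Youth SD (logits) | Mean reply rate, week 1 to week 12 | Coverage of nominal 95% CI | Youth-level fitted rates outside 0–1 |
|---|---|---|---|
| 1.0–1.2 | about .77–.83 to .58–.68 | 94.4–95.8% | 0.3–2.3% |
| 1.5 | .83 to .50 | 93.9% | 7% |
| 2.5 | .86 to .50 | 88.9% | 16% |

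Further runs with other start and end rates gave 93% at SD 1.5 to 2.0 with steep decay, and 90% with 15% of fitted values out of range at SD 2.5. With no trend, coverage was about 95%.

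**4. Effect on the test.** Rejection rates for the linear slope test and a logistic GEE were compared at SD 1.2 with a decline of 0.6 log-odds over the 12 weeks (200 trials per setting).

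| Base reply probability | Linear | Logistic |
|---|---|---|
| .50 | .67 | .67 |
| .70 | .62 | .62 |
| .85 | .58 | .57 |
| .93 | .47 | .49 |

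With no trend the rates were .05 to .075 (linear) and .05 to .08 (logistic). No fitted population mean left the range 0 to 1.

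**The case against.** The strongest case for leaving Section 17 alone has four parts.

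- Yes/no is not stated. Section 17 speaks of frequency and rates, Section 13 allows for up to just under 50 prompts in all, and Section 2 makes about two thirds of the texts group messages. This stands, and is why the variable must be defined.
- The narrow intervals need steep decay and large differences between youths, which no document supports. They also come from the variance structure rather than from linearity as such: basing the standard error on the between-youth variance of slopes restored coverage to 94.7–95.8% in every scenario tried. The random intercept is itself assumed for the reply model. All this stands, and it limits the harm.
- A reader might infer that .82 sits on the wrong model, because it is attached to linear models while the targets get generalized ones. The documents do not support that. The power sentence speaks of target engagement, the analysis is said to have evaluated the models just described, the linear mixed model is the Gaussian, identity-link case of the generalized one, and .82 reproduces for a continuous score.
- A reader might also infer that text compliance could pass as evidence that the targets moved. Section 2 does not list replies among the Aim 2 targets, and Section 17 gives each target its own model, so this is speculation.

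What remains is that the stated method for replies is not the natural one, that a better one costs nothing, and that Sections 2 and 17 place the outcome under different aims.

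**Conclusion.** The point holds in modest, conditional form. If a reply is coded yes/no per prompt and the linear model has only a youth intercept, trend intervals cover about 90 to 93% under youth SDs of 1.5 to 2.5 logits with steep decay. The harshest settings tried lie between 88 and 90%. Coverage is close to 95% with mild decay or no trend. Youth-level fitted rates leave the range 0 to 1 in roughly 7 to 16% of cases under steep decay, although the fitted population mean stayed in range wherever it was checked. The test for a decline is little affected, as checked at SD 1.2 with a mild decline. To say outright that the trend is mis-fitted would go too far.

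The change of aim between Sections 2 and 17, and the absence of any family or link, are on the page and need no assumption. The power sentence is loosely labelled and has not been shown to be wrong. The label has substance only for weekly contacts: under a count model, a power figure based on d does not carry over, and the documents give no mean, dispersion or rate ratio from which to compute one.

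**What to change.** In Section 17:

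1. Define the reply variable as the youth's own reply (yes/no) to each prompt, so that an adult's reply in a group text does not count.
2. Model it with a logistic mixed model (week fixed, youth random), and report predicted reply probabilities by week with intervals.
3. Report it under Aim 1, as Section 2 does, and amend the sentence that Aim 1 uses only descriptive statistics.
4. State family and link for each target: a linear (Gaussian) mixed model for the scale scores, and a generalized count model for weekly contacts.
5. Reword the power sentence so that .82 refers to the scale-score targets only, and state the sample size, alpha and waves behind it.

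The cost is plan wording. Data collection does not change, and standard mixed-model software fits all of these models.
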